4.6 Monitoring for subject compliance

The administration of the investigational product is performed in the laboratory overlooked by the clinical staff.

5 OUTCOME ASSESSMENTS

5.1 Gait ataxia (primary outcome):

Gait ataxia is assessed using biomechanical gait analyses. 3-D kinematic gait data is obtained using reflective markers, arranged in the Plug-in-Gait configuration and a 6-camera Motion Analysis System sampling at 100 Hz. Ground reaction forces and moments are obtained with two 6-channel force platforms operating at 1500 Hz. The participants walk a distance of 10m 25 times at self selected comfortable speed, while kinematic and kinetic data is recorded. 25 series of gait cycles will be recorded.

From the gait analyses gait ataxia is quantified as step-to-step variability. Ataxia is defined as increased (or excess) variability during normal walking.

CONFIDENTIAL

12

The analyses of gait ataxia are done at The Parker Institute, Copenhagen University Hospital at Frederiksberg.

5.2 Autonomous nerve system (secondary outcome):

The autonomic nervous control of heart rate and blood pressure will be analyzed through the use of quantitative test of maximal capacity as well as of ambient activity. Blood pressure and interbeat intervals will be recorded continuously on a beat by beat basis by CNAP-monitor (photoplethysmography) and by one standard precordial lead in the ECG. The maximal capacity will be quantified from the Valsalva manoeuvre primarily using the blood pressure response during phase 2 as a measure of sympathetic activity. Further quantification will be made by deep breathing test analyzing heart rate changes as a measure of parasympathetic function. The ambient activity will be measured from spontaneous fluctuations in heart rate through the use of both time and frequency analysis as well as by deterministic methods.

The analyses of autonomous nerve system are done at Syncope Center, Copenhagen University Hospital at Frederiksberg.

5.3 Plasma concentrations of opioid metabolites (secondary outcomes):

Blood samples are drawn from the cubital region every hour for 7 hours (7 samples) during each study visit. 10 ml is drawn at each time point (70 ml each visit, total 210 ml throughout the study). For storage of the samples a research bio-bank is established. The purpose of the bio-bank is to store the biological material safely and controlled until batch analyses can be performed. Once analyses have been completed, the material will be destroyed. The material is stored for a maximum 5 years and is subsequently destroyed – irrespective of whether analyses have been completed or not.

The analyses of plasma concentrations of active ingredients and metabolites are done at The Faculty of Pharma, University of Copenhagen.

5.4 Patient reported dizziness (secondary outcome; appendix F):

Current self reported dizziness is measured every hour for 7 hours (7 samples) during each study visit. Dizziness is measured using a Visual Analog Scale (VAS) ranging from 0–100 (0=no dizziness; 100=worst imaginable dizziness) with 101 point resolution on a validated electronic touch screen.

5.5 Knee pain (secondary outcome; appendix G):

Current knee pain is measured every hour for 7 hours (7 samples) during each study visit. The VAS for measuring pain intensity is an acceptable measure used in many chronic pain trials. This study will use a VAS ranging from 0-100 (0=no pain; 100=worst imaginable pain) with 101 point resolution on a validated electronic touch screen.

6 SAFETY

It is not expected that participation in the study will lead to significant risks or complications for the participants. The study drugs are approved in Denmark and are often used as pharmacological pain therapy. Risk of opioid dependencies with one opioid dosage (*Tapentadol* and *Tramadolhydrochorid*) is estimated not to exist.

CONFIDENTIAL

13

All assessments are performed by qualified staff with relevant education and training. Transportation to and from the research facility to the participants' home will be arranged, because the investigational agents are associated with impaired ability to drive a car (cf Summaries of Product Characteristics). Also, the participants are required to have an escort on their way from the research facility and not to be alone during the afternoon, evening and night following an assessment visit.

It is not expected that safety issues will occur that will lead to suspension or termination of the study.

6.1 Adverse Events (AE)

An AE is any untoward medical occurrence (e.g., sign, symptom, disease, syndrome, intercurrent illness) that occurs in a study subject following exposure to the study drugs, regardless of the suspected cause. Only subjects who have been exposed to a study drug can experience AEs. Untoward experiences occurring prior to first study drug administration (day 1) are part of past medical history.

Because this is an experimental study with only one exposure to each study drug no adverse events other than the outcomes mentioned in this protocol (gait ataxia and self reported dizziness) will be recorded.

The study drugs have been thoroughly tested for safety and adverse events and it is assumed that the adverse events profiles of the study drugs are well-described. Only event categorized as serious adverse reactions (SAR), serious adverse events (SAE) or unexpected serious suspected adverse reactions (SUSAR) will be recorded. According to Good Clinical Practice guidelines the following definitions are applied:

SAE (serious adverse event): A SAE is any untoward medical occurrence that at any dose

- Results in death.
- Is life-threatening
- Requires inpatient hospitalization
- Results in persistent or significant disability/incapacity,
- Is a congenital anomaly/birth defect, or
- Requires intervention to prevent permanent impairment or damage

SAR (serious adverse reaction):

- The event must be a SAE.
- There must be a certain degree of probability that the event is an adverse reaction to the administered drug.

SUSAR (suspected unexpected serious adverse reaction):

- The event must be a SAE.
- There must be a certain degree of probability that the event is an adverse reaction to the administered drug.
- The adverse reaction must be unexpected, i.e. not foreseen in the Summaries of Product Characteristics.

6.2 Adverse Event Reporting

The occurrence of any SUSAR leads to immediate reporting (as fast as possible – not later than 7 days (fatal or life-threatening SUSARs) and not later than 15 days (other SUSARs) after the sponsors has been informed) to the Danish Health and Medicines Authority using the appropriate electronic reporting system. SUSARs are also reported annually and at study termination to the Danish Health and Medicines Authority and the Health Research Ethics Committee.

	Danish Health and Medicines Authority		Health Research Ethics Committee	
SUSAR	Immediately	Yes*	Immediately	No
	At study termination	Yes	At study termination	Yes
SAR	Immediately	No	Immediately	No
	At study termination	Yes	At study termination	Yes
SAE	Immediately	No	Immediately	No
	At study termination	Yes	At study termination	Yes

^{*} As fast as possible – not later than 7 days (fatal or life-threatening SUSARs) and not later than 15 days (other SUSARs) after the sponsors has been informed.

6.3 Contraception

Female subjects of child-bearing potential and spouses or partners of male subjects of child-bearing potential must use contraception throughout study participation.

Appropriate contraceptive methods include hormonal contraceptives (oral, injected, implanted or transdermal), tubal ligation, intrauterine device, vasectomy, or double barrier methods. Abstinence is an acceptable form of birth control, though appropriate contraception must be used if the subject becomes sexually active. Sterile male partner or use of double barrier (condom in combination with diaphragm) is acceptable if usage is ensured. At the information interview potential participants are informed that usage of either of the investigational products is not recommended during pregnancy. Sterile or infertile females are not required to use contraception. To be considered sterile or infertile the female must generally be surgically sterilized (vasectomy/bilateral tubectomy, hysterectomy or bilateral ovarectomy) or be postmenopausal, defined as absence of menstruation at least 12 months before study enrolment.

Whether a potential female participant is fertile and whether she is sexually active is assessed by a medical doctor based on an interview at the screening visit. It is emphasized to the participant that in case the fertility status or sexual activity changes from being not present to present during the study, the participant must inform the investigator of this, in order to make appropriate consideration about contraceptives.

7 STATISTICAL PLAN

7.1 Statistical Methods

All data analyses will be carried out according to this prespecified analysis plan. Analyses are done applying SAS software (v. 9.2; SAS Institute Inc., Cary, NC, USA). The repeated measures of changes from the wash-out baseline assessment (hour 0 at each visit) are analyzed using a Repeated-Measures Analysis of Covariance (via PROC MIXED): a factor for

drug (Tapentadol, Tramadolhydrochlorid, and Placebo), a factor for time (hour; 6 levels), group (healthy controls and patients) drug-by-time, drug-by-group, group-by-time, and drug-by-time-by-group interactions, with the daily baseline values as covariates. Participants will be handled as a random factor.

In case of non-normal distribution, data transformation may be necessary.

Estimated least-squares mean effects over each individual Time point (Hours 1-6) will be reported for each drug and group. All estimated means will be presented with standard errors and 95% confidence intervals. For the differences between drugs, significance tests (p-values) will be shown.

Exploratory analyses are done with demographic variables and the secondary outcomes (plasma concentration of opioid metabolites, autonomous nerve system, pain and self-reported dizziness) as covariates, to assess the effects of these on the primary outcome.

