3.2 Primary Study Endpoints/Secondary Endpoints

Primary outcome:

- Change from the post-washout baseline in gait variability over time Secondary outcomes:
 - Change from the post-washout baseline in autonomous nerve system assessments over time
 - Change from the post-washout baseline in plasma concentrations of opioid metabolites over time
 - Change from the post-washout baseline in participant assessment of dizziness, nausea, and other adverse effects over time
 - Change from the post-washout baseline in knee pain (patients only) using 100 mm
 Visual Analogue Scale (VAS) over time

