3.5 Study Treatment

Tapentadol is administered as a single dose in a 50 mg formulation (Palexia Depot, Grünenthal). Tramadolhydrochlorid slow release is administered as a single dose in a 100 mg formulation (Mandolgin Retard, Sandoz). Inert placebo is administered as inert calcium tablets.

The tablets will be encapsulated to mask the tablets. The encapsulation will be performed at *Sygehusapotek Fyn, Odense Universitetshospital* according to GMP (Good Manufacturing Practice).

The tablets will be packed in triplets with one of each investigational product and one placebo. Each tablet will be packed in a small duma. On each duma, the number "1", "2" or "3" will be printed, to define the order of tablet administration. There will be an equal amount of each investigational product labeled "1", "2", and "3". A triplet of small dumas including one of each investigational products and one placebo will be packed together in a sealed labeled plastic container.

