4.2 Inclusion Criteria

Healthy subjects:

- In general good health, in the opinion of the Investigator, based on medical history and physical examination.
- Ability to comprehend and a willingness to provide written informed consent
- Age between 50 and 75 years
- No opioid usage 3 months prior to the study
- No musculoskeletal pain requiring medical attention during the previous 3 months
- Willing and able to complete study visits and procedures

CONFIDENTIAL

10

- Willing to hold activity, exercise level, and concurrent treatments/therapies generally consistent during the study
- A body mass index (BMI) of ≤30

Patients with knee osteoarthritis

- Diagnosis of knee OA
- Ability to comprehend and a willingness to provide written informed consent
- Age between 50 and 75 years
- No opioid usage 3 months prior to the study
- Knee pain of at least 40 mm on a 0-100 mm visual analog scale (without analgesics) representing the average pain intensity during the previous week
- Willing to discontinue all pain medications 24 hours before and during examination visits
- Willing and able to complete study visits and procedures
- Willing to hold activity, exercise level, and concurrent treatments/therapies generally consistent during the study
- In general good health, in the opinion of the Investigator, based on medical history and physical examination.
- A body mass index (BMI) of ≤30

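### The common change-from-baseline model does not suit plasma concentration, which is zero by design at every hour 0 and every placebo visit

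*Protocol*

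**What the plan says.** Section 3.2 lists among the secondary outcomes: "Change from the post-washout baseline in plasma concentrations of opioid metabolites over time". It has the same form as the primary outcome.

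Section 7.1 opens with "All data analyses will be carried out according to this prespecified analysis plan" and then describes one response model: "The repeated measures of changes from the wash-out baseline assessment (hour 0 at each visit) are analyzed using a Repeated-Measures Analysis of Covariance". The first two factors are "drug (Tapentadol, Tramadolhydrochlorid, and Placebo), a factor for time (hour; 6 levels"; group and all interactions follow, "with the daily baseline values as covariates". Participant is the only random term named. Least-squares means with standard errors and 95% confidence intervals are promised for each drug, group and hour, with p-values for differences between drugs. On distribution, the section says only: "In case of non-normal distribution, data transformation may be necessary". It describes no separate response model for plasma, and it also lists plasma as an exploratory covariate for the primary outcome.

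Four design facts bear on the plasma values:

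- Section 3.5: "Inert placebo is administered as inert calcium tablets".
- Section 4.2, both groups: "No opioid usage 3 months prior to the study".
- Section 3.1: the hour-0 measurements precede the tablet.
- Section 1.4: visits are at least 7 days apart.

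Section 5.3 has blood drawn hourly at each visit, placebo visits included, and assays both active ingredients and metabolites.

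**The concern.** Sections 3.2 and 7.1, read together, put plasma concentration under the common model. Gait variability or a dizziness score varies at baseline and on placebo, so that model can make sense for them. Plasma concentration does not vary there. A participant who has had only calcium has no study opioid to measure, and neither does one who has not yet been dosed that day.

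Three things follow. The hour-0 covariate carries no information. A comparison with placebo tests something already known. And placebo cells with no spread are modelled together with active-drug cells whose spread grows with concentration. If all share one residual variance, the standard errors for the active drugs are diluted by the zeros. At stake are the plasma means and intervals by hour and group, which describe the exposure behind any gait effect.

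**Working it through.** **1. Is hour 0 really zero?** The documents give no half-life. Assuming 4 to 12 hours, the fraction left after 7 days (168 h) is 0.5^(168/4) = 2 × 10⁻¹³ to 0.5^(168/12) = 6 × 10⁻⁵. Zero is a fair description.

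**2. The covariate.** Drug (3) × hour (6) × group (2) gives 36 cell means. The baseline makes 37 columns, but for plasma that column is all zeros and the design matrix has rank 36. The slope cannot be estimated, software drops it, and the rest of the model fits. Change from baseline then equals concentration.

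**3. The intervals under one residual variance.** Each participant has 3 visits × 6 hours = 18 values. Let vb be the participant variance and ve the residual variance. In balanced data their estimates sum, in expectation, to the average of the 18 cell variances. With 12 per group, the model's variance for a cell mean is (vb + ve)/12; the true variance is that cell's own variance divided by 12. Hence

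SE ratio (model/true) = √(average cell variance / own cell variance), and approximate coverage = 2Φ(1.96 × ratio) − 1.

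*Flat profile, so that the zeros are the only cause.* Let an active cell have variance t.
- One analyte: 6 of 18 cells are non-zero, so the average is t/3, the ratio √0.333 = 0.577 and coverage 74%. In components, with between-person variance dominating: ve = 4t/17 = 0.235t and vb = (2t − 0.235t)/18 = 0.098t, which sum to 0.333t.
- Each drug's own analyte in one model: 12 of 18 cells are non-zero, the average is 2t/3, the ratio 0.816 and coverage 89%.

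*Rising profile.* Assume means of 0.3, 0.6, 0.85, 1, 1 and 0.95 of peak at hours 1-6, with SD proportional to the mean. The squares sum to 4.075.

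| | Average variance (peak = 1) | Hour 1 ratio | Hour 3 ratio, coverage | Hours 4-5 ratio, coverage | Hour 6 ratio, coverage |
|---|---|---|---|---|---|
| One analyte | 4.075/18 = 0.226 | 1.59 | 0.56, 73% | 0.48, 65% | 0.50, 67% |
| Both drugs' analytes | 8.15/18 = 0.453 | 2.24 | 0.79, 88% | 0.67, 81% | 0.71, 84% |

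*Simulation.* The model was simulated with 12 per group, a participant random intercept, one residual variance and log-normal levels. The settings were a coefficient of variation of 30-80%, or a between-person log SD of 0.3-0.5 with a within-visit SD of 0.1-0.2, and more than one rising profile. Coverage of the active-drug mean was about 62-71% for one analyte and 80-87% with both drugs' analytes, over hours 3-6 or 4-6 depending on the run. With a flat profile it was 72-74% and 88-90%. For active minus placebo, coverage was about 74-82% and 85-93%.

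**4. Width on a concrete scale.** With a peak mean of 100 and a coefficient of variation of 50%, the half-width at hours 4-6 from each cell's own variance is about 29-30. The common model gives about 20 with both drugs' analytes and about 14 with one. Placebo, whose interval should have width zero, receives the same ±20 or ±14.

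**5. Transformation.** If a log were chosen, placebo zeros would need an offset. With an active mean of 100, offsets of 0.01, 0.1, 1 and 10 give an active-placebo difference on the log scale of 9.1, 6.8, 4.5 and 2.3. The answer is set by the offset, and placebo still has no variance.

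**The case against.** Several points limit this concern, and most of them stand.

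- **Residual variance.** A reader might infer that the intervals are wrong whatever is done. The protocol does not support that. Section 7.1 names PROC MIXED and a participant random factor; it neither states nor excludes a variance by drug or hour, and a statistical analysis plan may supply one. Doing so would reduce the interval error, but would not make the covariate or the placebo contrast informative.
- **Log transformation.** A reader might infer that the plan prescribes an impossible log. It names no particular transformation and only allows for one.
- **Empty covariate.** It does not break the model. It drops out, and change from zero gives the right number.
- **Placebo tests.** Section 7.4 confines testing at the 0.05 level to the two investigational products. The wording in 7.1 on differences between drugs can be read to include placebo, since placebo is a level of that factor, but this is not a clear commitment to such tests.
- **Scope.** Section 7.1 does not name plasma as a response. Its inclusion follows from 3.2, from the statement that all analyses follow this plan, and from the reference in 7.4 to all endpoint analyses. That reading is sound but is an inference. Use as an exploratory covariate is an additional role and does not exempt plasma.
- **Size.** The lowest coverage needs one analyte modelled across all three visits, a set-up that the protocol does not spell out. The variances and profiles are assumed, and the hour-1 excess depends on the assumed curve: a less steep profile gives hour-1 coverage near 95% for a single analyte.

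What does not stand is that this is merely a detail left open. The protocol fixes the placebo level, the hour-0 covariate and the reported intervals, and these suit plasma badly.

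**Conclusion.** The concern holds in a conditional form. As written, 7.1 gives plasma a model whose covariate is empty and whose placebo level is a known zero. Under a single residual variance, active-drug intervals are too narrow from about hour 3, with the coverage shown above, and placebo gets an interval of non-zero width around zero. The direction for active-drug means at the later hours was the same in every setting tried; the exact figures rest on assumed log-normal levels, spread and profile, for which the protocol gives no values.

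The effect is confined to one secondary outcome. It would be wrong to carry it over to the primary gait analysis or the sample size, since gait variability is not structurally zero on placebo or at hour 0. The text should be changed, but the main result of the trial does not depend on it.

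**What to change.** In 7.1, exempt plasma concentration from the common model and state instead:

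- Analyse each analyte only at the visits where its own drug was given, hours 1-6.
- Use hour and group as factors, with a covariance across hours that lets the variance differ by hour.
- Work preferably on the log scale, with a stated rule for values below quantification. These may occur at hour 1, as both products are extended release.
- Use no hour-0 covariate and make no placebo contrast.
- Keep the hour-0 and placebo-visit samples as a check for carry-over and dosing errors.

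Restating the outcome in 3.2 as concentration at hours 1-6 would be clearer but is optional.

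The cost is a few sentences, with no new samples, visits or assays. The one small loss is that no drug-versus-placebo p-value is reported for plasma, and such a p-value carries no information.

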3.1 Study Design/Type

The study is designed as an experimental single center, double-blind treatment, cross-over study with inert *placebo*, *Tapentadol* (Palexia Depot), and *Tramadolhydrochlorid* (Mandolgin Retard), with a minimum of 7days wash-out periods.

At day 1 (Visit 1), baseline measurements are carried out before tablet administration. Immediately after baseline measurements one tablet is administered, and hourly measurements are performed for 6 hours. Subsequently all participants enter a minimum 7 day washout period, after which they return to the facility to repeat the procedures at Visit 2 (day 8+) and Visit 3 (day 15+). The order of treatments will be randomized (1:1:1). The design is illustrated below:

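### Section 7.1 names participant as the only random factor, so drug tests that pool over the hours of a visit get standard errors that are too small if the model is fitted as written

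*Protocol*

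**What the plan says.** Section 3.1 describes the measurement schedule for one visit: "Immediately after baseline measurements one tablet is administered, and hourly measurements are performed for 6 hours". This is repeated at three visits, and section 1.4 gives one tablet per visit.

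Section 7.1 presents itself as the prespecified analysis plan. Changes from each visit's hour-0 value are to be "analyzed using a Repeated-Measures Analysis of Covariance (via PROC MIXED): a factor for" drug, followed by "a factor for time (hour; 6 levels), group (healthy controls and patients) drug-by-time, drug-by-group, group-by-time, and drug-by-time-by-group interactions", and each visit's own baseline enters as a covariate. The random part is one sentence: "Participants will be handled as a random factor". Visit appears neither as a fixed nor as a random term, and no covariance structure is named for the hours within a visit.

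For reporting, 7.1 says: "Estimated least-squares mean effects over each individual Time point (Hours 1-6) will be reported for each drug and group". It adds: "For the differences between drugs, significance tests (p-values) will be shown". It does not say whether those p-values are per hour, averaged over hours, or both. Section 7.4 sets the 0.05 level for comparing the two active products on all endpoints.

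**The concern.** Each participant contributes 3 visits × 6 hours = 18 post-dose values, so 24 completers give 432 values. Only 24 × 3 = 72 participant-visits received a drug. A random participant intercept gives all 18 values of a person one common correlation. It makes no allowance for whatever makes one day differ from another, such as the participant's state or markers applied afresh.

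Any such day effect moves all six hourly values of a visit together and is confounded with that visit's drug within the participant. A test that pools the hours then counts one day's deviation about six times over. The drug main effect, drug-by-group and any hour-averaged drug contrast would be judged against too small an error, and a drug difference could be declared where none exists.

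**Working it through.** **The protocol's own power figure.** Section 7.2 states 80.4% power for a difference of 0.03 with 24 participants, without an SD. A two-sided paired t-test with n = 24 and an SD of the within-participant difference of 0.05 gives 80.37%; solving backwards gives SD = 0.050. The figure therefore fits one paired difference per participant, on 23 df. The model in 7.1, fitted with a participant intercept only, has 432 values − 37 fixed parameters (3 × 6 × 2 cells plus baseline) − 22 for participants within groups = 373 residual df.

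**Why pooling goes wrong.** Let *s* be the visit-to-visit share of within-participant variance, with total within-participant variance set to 1. The documents do not give *s*; it is assumed. Leave the baseline covariate aside for the moment.

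- True variance of a six-hour visit mean: *s* + (1 − *s*)/6 = (1 + 5*s*)/6.
- Residual variance that the participant-only model estimates: each participant has 17 within-person df, 2 between visits with expectation 6*s* + (1 − *s*) and 15 within visits with expectation 1 − *s*. The average is (1 − *s*) + (12/17)*s* = 1 − 0.294*s*. The model takes the variance of a visit mean as one sixth of this.
- Ratio of true to assumed variance: R = (1 + 5*s*)/(1 − 0.294*s*).
- Approximate type I error: pairwise 2[1 − Φ(1.96/√R)]; 2-df drug test exp(−5.991/(2R)).

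| *s* | R | Pairwise | 2-df test |
|---|---|---|---|
| 0 | 1.00 | 5.0% | 5.0% |
| 0.1 | 1.55 | 11.5% | 14.4% |
| 0.2 | 2.13 | 17.9% | 24.4% |
| 0.3 | 2.74 | 23.7% | 33.5% |
| 0.5 | 4.10 | 33.3% | 48.2% |

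**Simulation with the baseline covariate.** Null trials used 24 participants, 3 visits and 6 hours, the full drug × time × group factorial, each visit's baseline as covariate, a REML participant intercept and residual df (1,500 to 3,000 trials per setting below). Two versions of the visit effect were tried.

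| *s* | Visit effect also in hour 0: pairwise / 2-df | Visit effect after dosing only: pairwise / 2-df |
|---|---|---|
| 0 | 6.0% / 6.0% | 5.9% / 6.0% |
| 0.1 | 12.1% / 15.7% | 11.8% / 15.7% |
| 0.2 | 17.1% / 22.3% | 17.0% / 24.6% |
| 0.3 | 21.0% / 29.0% | 24.1% / 35.0% |
| 0.5 | 25.7% / 35.7% | 33.3% / 48.6% |

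The right-hand columns match the algebra. In the left-hand columns the daily baseline carries part of the visit effect and absorbs some of the inflation, but far from all. Further runs of the first kind gave up to 37% for the 2-df test. A 500-run set gave 13-41% for drug-by-group over *s* = 0.1 to 0.5.

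**Tests that are not affected in this way.**

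- Drug difference at one hour: true-to-assumed variance is 1/(1 − 0.294*s*), which is 1.17 at *s* = 0.5, so the error is about 7.0%. Simulated at hour 3: 4.5 to 9%.
- Drug-by-time: the true error variance is 1 − *s*, against the assumed 1 − 0.294*s*. At *s* = 0.5 the ratio is 0.5/0.853 = 0.59, so the test is conservative. Simulated: 5.3% at *s* = 0, falling to 0.1% at *s* = 0.5.

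**After the fix.** The same data analysed as visit means with participant, drug, drug-by-group and baseline (72 − 29 = 43 error df) rejected in 4 to 6% of null trials in every setting, including AR(1) correlation of 0.3 to 0.9 within visits.

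**The case against.** Four points can be made against this.

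- **The covariance is unstated rather than wrongly stated.** A repeated-measures model in PROC MIXED may carry a REPEATED covariance, and a statistical analysis plan, which was not available for this review, may specify one. This stands in part and is why the point is conditional on the model being fitted as written. But 7.1 calls itself the prespecified plan and names one random factor. A REPEATED statement helps only if it gives hours of the same visit extra correlation; compound symmetry over all of a participant's values would reproduce the problem.
- **The committed outputs are hour by hour.** The least-squares means promised in 7.1 are per hour, and those contrasts stay near nominal. This stands and limits the point. It does not remove it: drug and drug-by-group are model terms, and the promised p-values are not confined to single hours.
- **No visit variance is given.** A reader might infer a fixed multiple of the nominal error rate. The documents do not support that: the rate is about nominal at share 0, at share 0.05 about 8-10% pairwise and 10-11% for the 2-df test, and it differs by test.
- **Shared hour-0 error.** A reader might also blame the baseline error common to all six change scores. With the daily baseline as covariate, a change-score model equals a model of the raw value with the baseline slope shifted by 1, and the runs at share 0 show no inflation from this source.

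**Conclusion.** The point holds conditionally. If 7.1 is fitted with a participant random effect alone, drug tests that pool over hours are anti-conservative. With a visit-to-visit share of 10 to 50% that also affects the hour-0 value, type I error is about 15-37% for the 2-df drug test, 13-41% for drug-by-group and 12-26% for the pairwise hour-averaged contrast. If the visit effect arises only after dosing, the upper ends for the drug test and the pairwise contrast rise to about 49% and 33%. The share is an assumption; a share of exactly zero is hard to credit for visits at least a week apart with markers reapplied.

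The drug-by-group range rests on only 500 runs per setting and is the least precise. A reader might conclude that the whole primary analysis is unsound. That goes too far: hour-specific contrasts stay at about 5-9% and drug-by-time errs on the safe side.

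**What to change.** In section 7.1, add a random participant-by-visit effect alongside the random participant effect, with Kenward-Roger degrees of freedom.

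An alternative is an unstructured covariance over the six hours with subject = participant*visit, again with the random participant. If AR(1) or Toeplitz is used as a fallback, keep the participant-by-visit effect as well. AR(1) alone decays and understates a constant day effect: at correlation 0.3, the variance of the six-hour mean is (1 + 5 × 0.3)/6 = 0.42 under a constant effect but about 0.28 under AR(1). The hour-averaged test would then still reject at 2[1 − Φ(1.96/√(0.42/0.28))], about 11%.

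The cost is one line of PROC MIXED code and one sentence in 7.1. Intervals for hour-averaged drug effects become wider, which is correct; no design or data-collection change is needed.
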